### **5.3. Study Population Diversity**

The Sponsor will select clinical sites to support recruitment of a diverse and representative population, including older individuals and racial and ethnic minorities.

## **6. STUDY INTERVENTION**

### **6.1. Study Intervention(s) Administration**

#### **6.1.1. Study Intervention Description**

NTZ 300 mg extended release tablets for use in this study are yellow, round, convex, film-coated, bi-layer tablets for oral administration, each tablet contains 300 mg of NTZ and the inactive ingredients.

Placebo tablets will have the same appearance and inactive ingredients as the active NTZ 300 mg extended release tablet.

The vitamin B complex supplement is Super B-Complex™ manufactured by Igennus Healthcare Nutrition, Cambridge, UK. The supplement will supply each subject with the following Percent Daily Values based on a 2,000-calorie diet: vitamin B1 1,333%, vitamin B2 824%, vitamin B3 240%, vitamin B5 360%, vitamin B6 1000%, vitamin B7 100%, vitamin B12 15,000%, folate 100%, and vitamin C 267%.

#### **6.1.2. Dosing and Administration**

Group 1 (NTZ): Subjects will receive two NTZ 300 mg tablets b.i.d. with food (< 1 hour after food intake) and a B complex vitamin (Super B-Complex™, Igennus Healthcare Nutrition, Cambridge, UK) b.i.d. for 5 days

**Group 2 (Placebo):** Subjects will receive two placebo tablets b.i.d. with food (< 1 hour after food intake) and a B complex vitamin (Super B-Complex™, Igennus Healthcare Nutrition, Cambridge, UK) b.i.d. for 5 days

The food prior to drug intake should preferably be a high-fat meal, but at minimum a cereal bar.

All subjects will receive a vitamin B complex supplement one tablet twice a day (manufacturer's labeled dosing) to help mask any potential chromaturia attributed to NTZ and aid in maintaining study blinding.

## 6.2. Preparation, Handling, Storage and Accountability

### 6.2.1. Acquisition and Accountability

Study medication will be provided by the Sponsor to the Investigational Site for dispensing.

Drug accountability will be tracked using an IWRS/IRT system as described in the study-specific Data Management Plan. Unused supplies must be returned to the Sponsor or destroyed in accordance with institutional procedures in effect at the study Site.

### 6.2.2. Packaging and Labeling

NTZ or placebo tablets will be packaged in white 30 cc HDPE bottles, each containing 20 tablets. The kits will be stored at room temperature and will bear labels with the following information:

**Table 4: Study Medication Label**

20 Tablets	Study No. RM08-3008	Treatment No: XXXX
Lot No: XXXX		
Take 2 Tablets by Mouth with Food Twice Daily		
Caution: New Drug – Limited by Federal Law to Investigational Use		
STORE AT ROOM TEMPERATURE • DO NOT USE BEYOND END OF STUDY		
KEEP OUT OF REACH OF CHILDREN		
Study Sponsor: The Romark Institute for Medical Research		
[Redacted]		

## 6.3. Randomization and Blinding

Subjects will be randomized 1:1 to receive either NTZ or placebo. An independent third party will prepare a master randomization list and maintain the masking of the study. Subjects who qualify for the study will be assigned to treatment using centralized randomization procedures. The treatment numbers will appear on the bottles containing the masked study medication. The randomization list will be masked to study participants including Sponsor, Investigators, study monitors, statisticians, subjects and laboratory personnel. Unmasking procedures will be detailed in the Medical Monitoring Plan and Investigators will be provided instructions for unmasking.

## 6.4. Study Intervention Compliance

Subject compliance with study medication will be checked by site staff daily during the treatment period. Subjects will return the treatment kit with any unused medication to the clinic at the Day 10 visit. Subjects will be considered non-compliant (major protocol deviation) if they have missed more than two doses of the study medication during the first three days of the study. Non-compliance will not be cause for discontinuation of subject participation in the study.

## 6.5. Concomitant Therapy

The following medications will not be allowed during the study: topical or systemic decongestants, nasal corticosteroids, and any prescription or non-prescription medications classified as (i) expectorants and cough preparations, (ii) analgesics and antipyretics, (iii) antihistamines (American Hospital Formulary Service (AHFS) classification) or (iv) medications considered major CYP2C8 substrates (see [Table 5](#) below). As an exception to this rule, subjects will be allowed to use acetaminophen and/or dextromethorphan as necessary for disabling symptoms.

**Table 5: Major CYP2C8 Substrates**

Generic Name	Brand Name(s)	Therapeutic Use and/or Drug Class
Amodiaquine	BASOQUIN, CAMOQUIN, FLAVOQUIN	Antimalarial
Daprodustat (GSK1278863)	*	Antianemic, prolyl hydroxylase inhibitor
Dasabuvir (ABT-333)	EXVIERA	Antiviral, NSB5 inhibitor
Enzalutamide	XTANDI	Anticancer, antiandrogen
Montelukast	SINGULAIR	Antiasthmatic, LTRA
Pioglitazone	ACTOS	Antidiabetic, PPAR- $\gamma$ agonist
Repaglinide	NOVONORM, PRANDIN	Antidiabetic, meglitinide analog

Source: Backman et al. 2016

\*Currently listed as investigational only and not yet granted a trade name by the manufacturer

Subjects are also prohibited from taking hydroxychloroquine, chloroquine, remdesivir, azithromycin or lopinavir/ritonavir during the study except as standard-of-care rescue medication.

Medications for pre-existing conditions that are not excluded (see exclusion criteria) should be continued as prescribed. Standard-of-care rescue medication is permitted for complications of COVID-19 illness. The use of such medication will be recorded in the EDC system.

## 7. STUDY INTERVENTION DISCONTINUATION AND PARTICIPANT DISCONTINUATION

Treatment will be discontinued for individual subjects for the following reasons:

1. An allergic reaction occurs or is suspected.

2. Medical conditions that may require study medication discontinuation in the Investigator's judgment.
3. Subject desire to discontinue participation.

In the case of an allergic reaction or other medical condition requiring subject discontinuation, appropriate treatment will be instituted by the Investigator.

Subjects will be encouraged to complete all protocol-specified follow-up visits even if study drug is withdrawn.

## **8. STUDY PROCEDURES**

### **8.1. Visit Procedures**

Study procedures to be completed at each visit are indicated in the [Schedule of Assessments](#). Descriptions of selected procedures are outlined in the following sections.

#### **8.1.1. Informed Consent**

Each subject must give written consent according to local requirements after the nature of the study has been fully explained. The informed consent form (ICF) must be signed before performance of any study-related activity. The informed consent form will be approved by both the Sponsor and by the reviewing IRB. They will be in accordance with principles that originated in the Declaration of Helsinki, current ICH and GCP guidelines, applicable regulatory requirements, and Sponsor policy.

Before enrollment in the study, the Investigator or an authorized member of the investigational staff must explain to potential subjects the aims, methods, reasonably anticipated benefits, and potential hazards of the study, and any discomfort participation in the study may entail. Subjects will be informed that their participation is voluntary and that they may withdraw consent to participate at any time. They will be informed that choosing not to participate will not affect the care he/she will receive. Finally, they will be told that the Investigator will maintain a subject identification register for the purposes of long-term follow-up if needed and that their records may be accessed by health authorities and authorized Sponsor staff without violating the confidentiality of the subject, to the extent permitted by the applicable law(s) or regulations. By signing the ICF the subject is authorizing such access, and agrees to allow his or her study physician to re-contact the subject for the purpose of obtaining consent for additional safety evaluations, if needed. Only subjects who are fully able to understand the risks, benefits, and potential AEs of the study, and provide their consent voluntarily will be enrolled.

The subject will be given sufficient time to read the ICF and the opportunity to ask questions. After this explanation and before entry into the study, consent should be appropriately recorded by means of the subject's personally dated signature. After having obtained the consent, a copy of the ICF must be given to the subject.

If the subject is unable to read or write, an impartial witness should be present for the entire informed consent process (which includes reading and explaining all written information) and should personally date and sign the ICF after the oral consent of the subject is obtained, if permitted by local law.

Assent from any minor ( $\leq 18$  years of age or as local regulations apply) enrolled into the study will be obtained along with documented consent from their parent/legal guardian to allow the minor to participate in the study. The assent and consent forms must be signed prior to the performance of any study related activity.

Signed ICFs must remain in the subject's file(s) and be available for verification by representatives of Romark, the IRB, and FDA/relevant regulatory agencies at any time.

### **8.1.2. Medical History**

All relevant medical history should be entered in the EDC system at the Screening visit. Relevant medical history includes:

1. Any disease, condition or surgery active at the time of the Screening visit;
2. Any disease, condition or surgery ending within two months of the Screening visit; or
3. Any other disease, condition or surgery relevant to the subject's infection or clinical management.

### **8.1.3. Physical Examination**

Physical examinations will include assessment of each body system including skin, head (eye, ear and nose), neck, mouth/throat, lymph nodes, cardiovascular, respiratory, gastrointestinal, neurological, and musculoskeletal systems as well as general appearance for abnormalities.

The Investigator will complete a full physical examination at the Screening visit. Physical examinations should occur at follow-up and unscheduled visits as required by symptoms or adverse changes from baseline.

### **8.1.4. Body Measurements and Resting Vital Signs**

Body measurements and resting vital signs will include assessment of the following:

1. Height (Screening visit only)
2. Weight
3. Oral temperature
4. Blood pressure
5. Pulse rate
6. Respiratory rate
7. Oxygen saturation

### **8.1.5. Screening FLU-PRO**

The FLU-PRO questionnaire will be administered during the Screening visit to confirm symptoms required for eligibility.

### **8.1.6. Randomization and Dispensing Study Medication**

Randomization and study medication kit assignment will be accomplished using an Interactive Randomization Tool (IRT) feature in the EDC system after all screening procedures have been completed and the subject has been determined to be eligible for the study. Site staff will witness the subject take the first dose of study medication in the clinic as soon as possible following randomization and record the date and time of medication intake in the EDC system.

### **8.1.7. Subject Instructions**

At each subject contact, site staff will instruct the subject regarding:

1. *Administration of study medication.* Subjects will be instructed to take the study medication (two tablets) twice daily with the morning and evening meals, approximately every 12 hours (< 1 hour after food intake, preferably a high-fat meal but at a minimum a cereal bar) and a B complex vitamin (Super B-Complex™, Igennus Healthcare Nutrition, Cambridge, UK).
2. *Completion of subject diary.* Subjects will be reminded to complete the electronic diary and any questions will be answered.
3. *Use of birth control.* Female subjects of childbearing potential, if sexually active, will be instructed to continue an acceptable method of birth control for the duration of the study and for 1 month post-treatment. Acceptable methods of birth control include a double barrier method, oral birth control pills, an IUD, or medroxyprogesterone acetate administered intramuscularly.
4. *Follow-up visits.* Subjects will be reminded of the study schedule and of the next scheduled visit.
5. *Seeking emergency care or contacting the study physician or nurse.* Subjects must be informed to seek emergency medical care or contact the study physician or nurse if they develop any of the following symptoms listed below at any point during the study.

**CONTACT STUDY PHYSICIAN IF YOU HAVE:**

- Trouble breathing including shortness of breath
- Severe headache, stiff neck, confusion or excessive somnolence
- If fever ( $\geq 99^{\circ}\text{F}$  or  $\geq 37.2^{\circ}\text{C}$ ) returns after being absent for 24 hours
- Increased difficulty breathing
- Wheezing develops
- New pain develops or pain localizes to one area, such as an ear, the throat, the chest, or the sinuses
- Symptoms become more severe or frequent
- Symptoms recur or any difficulty breathing following 5-10 days resolution of illness
- An allergic-like reaction occurs or is suspected
- Abnormal behavior

### **8.1.8. Day 2-7 Subject Contact**

Site staff will contact each subject by telephone on study Days 2-7 to verify:

1. Did the subject take all expected doses of study medication?
2. Did the subject complete all expected electronic diaries?
3. Does the subject have worsening symptoms or adverse events that warrant an unscheduled visit?
4. Does the subject have shortness of breath at rest? *If yes, instruct the subject to come to the clinic for an unscheduled visit to screen for progression of illness or refer to hospital as warranted. If the subject is referred to the hospital or emergency department, the Investigator will attempt to obtain hospital records indicating SpO2 or PaO2/FiO2 from the subject for the purposes of defining progression to severe COVID-19 illness. The SpO2 or PaO2/FiO2 obtained from hospital records will be entered on an Unscheduled Visit eCRF.*

If the subject has missed medication or electronic diaries, the site staff will re-train the subject on the importance of medication and diary compliance.

This contact may occur at the Day 4 or unscheduled visit in lieu of telephone contact.

### **8.1.9. Day 28 Subject Contact**

Site staff will contact each subject by telephone on study Day 28 to determine if the subject has experienced any new adverse events, developed severe COVID-19 illness, or required hospitalization for any reason.

If warranted, the Day 28 subject contact may also occur in-person at the clinic or another location as agreed upon by the site and subject.

## **8.2. Laboratory Assessments**

### **8.2.1. Assessments in the Clinic**

A urine pregnancy test will be performed in the clinic only for women of childbearing potential (post-menarche, pre-menopause, not surgically sterile) at the Screening visit.

### **8.2.2. Central Laboratory Assessments**

A central laboratory will be used for safety, diagnostic virology, and serology testing. A laboratory manual will be provided to each clinical site with sample collection and handling details.

#### **8.2.2.1. Laboratory Safety Assessments**

Blood tests for safety monitoring will include hemoglobin, hematocrit, complete blood count (total and differential), platelet count, random blood sugar, total cholesterol, HDL, LDL, triglycerides, albumin, AST, ALT, GGT, alkaline phosphatase, bilirubin (total/direct), BUN, creatinine, sodium, potassium, chloride.

Routine urinalysis will include appearance, glucose, protein, and blood.

### **8.2.2.2. Diagnostic Virology Testing**

Diagnostic virology testing will be performed using nasopharyngeal swab samples collected at the Baseline, Day 4 and Day 10. The nasopharyngeal sample for virology testing will be collected using a single nasopharyngeal swab inserted into both nostrils in accordance with procedures detailed in the study-specific laboratory manual.

The ePlex® Respiratory Pathogen Panel (“ePlex RPP”, GenMark, Carlsbad, CA) will be used to detect influenza A (non-specific as to subtype); influenza A H1, H1N1 (2009), H3 subtypes; influenza B; RSV A and B; parainfluenza 1, 2, 3 and 4; hMPV; adenovirus; human EV/RV; coronavirus NL63, HKU1, 229E and OC43; Chlamydophila pneumoniae; and Mycoplasma pneumoniae.

The Aptima® SARS-CoV-2 Assay (Hologic, Inc, San Diego, CA) will be used to detect SARS-CoV-2.

All Baseline nasopharyngeal swabs will be tested by the ePlex RPP and Aptima® SARS-CoV-2 assays. If the Baseline nasopharyngeal swab is positive for SARS-CoV-2, the Day 4 and 10 nasopharyngeal swabs will be tested for SARS-CoV-2. If the Baseline nasopharyngeal swab is positive for EV/RV, the Day 4 and 10 nasopharyngeal swabs will be tested using the ePlex RPP.

### **8.2.2.3. Quantitative Virology Testing**

Nasopharyngeal swab samples testing positive for SARS-CoV-2 will be subjected to quantitative RT-PCR for analysis of quantitative changes in viral RNA.

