## 3. STUDY OBJECTIVES

**Primary Objective:** To evaluate the effect of NTZ in reducing the time to Sustained Response compared to placebo in subjects with mild or moderate COVID-19

**Secondary Objective:** To evaluate the effect of NTZ in reducing the rate of progression to Severe COVID-19 Illness compared to placebo

**Exploratory Objectives:** To evaluate:

- The proportion of subjects positive for SARS-CoV-2 by Aptima® SARS-CoV-2 Assay at each of Days 4 and 10
- The change from baseline in quantitative SARS-CoV-2 RNA measured by RT-PCR at each of Days 4 and 10
- The effect of NTZ in reducing the rate of hospitalization compared to placebo
- The effect of NTZ in reducing the rate of mortality compared to placebo

Safety Objectives: Safety will be assessed by analysis of adverse events.

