#### 9.4.1. Efficacy Analyses

Efficacy analyses will be based on a population consisting of all subjects randomized who receive at least one dose of study medication and are positive for SARS-CoV-2 by Aptima® SARS-CoV-2 Assay at Baseline. For time-to-event analyses, a test of significance (as described in the following) will be performed with descriptive statistics provided, including the use of Kaplan-Meier figures.

There will be one primary efficacy analysis:

- Time to Sustained Response for the NTZ treatment group will be compared to that of the placebo treatment group using a stratified Gehan-Wilcoxon test ( $\alpha=0.05$ ) where stratification will follow that used for randomization. Subjects without a Sustained Response recorded will be treated as censored as of the last diary without a documented Sustained Response, except for subjects who are hospitalized or die during the study, who will be censored at Day 21 (hour 504).

Sensitivity analyses for the primary efficacy analysis will be described in the Statistical Analysis Plan.

If the primary analysis is significant at the 0.05 level, the key secondary efficacy analysis will be formally evaluated at the 0.05 level as follows:

- Proportions of subjects progressing to Severe COVID-19 Illness will be compared between the treatment groups using a Cochran-Mantel-Haenszel (CMH) test stratified by the randomization strata.

Exploratory analyses will be performed as follows:

- Proportions of subjects positive for SARS-CoV-2 by Aptima® SARS-CoV-2 Assay at study Day 4 and Day 10 will be compared between the treatment groups using a Cochran-Mantel-Haenszel (CMH) test stratified by the randomization strata.
- Mean changes from baseline in quantitative SARS-CoV-2 RNA measured by RT-PCR at Day 4 and Day 10 will be compared using a t-test.
- Proportions of subjects hospitalized due to COVID-19 or complications thereof will be compared across the treatment groups using a CMH test stratified by the randomization strata.
- Proportions of subjects with mortality related to COVID-19 or complications thereof will be compared across the treatment groups using a CMH test stratified by the randomization strata.

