4.1.2 Key Secondary and Exploratory Efficacy Variables

The key secondary efficacy variable is Progression to Severe COVID-19 Illness. Any subject meeting both of the following criteria has advanced to Severe COVID-19 Illness:

1. Shortness of breath at rest.
2. $\text{SpO}_2 \leq 93\%$ on room air, or $\text{PaO}_2/\text{FiO}_2 < 300$.

The exploratory efficacy variables are:

1. Proportion of subjects positive for SARS-CoV-2 by Aptima® SARS-CoV-2 assay at Days 4 and 10.
2. Change from baseline of quantitative SARS-CoV-2 RNA measured by RT-PCR at Days 4 and 10.
3. Hospitalization due to COVID-19 or complications thereof.
4. Mortality due to COVID-19 or complications thereof.

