Viral RNA levels will be determined for the Day 4 and Day 10 nasopharyngeal swabs by quantitative RT-PCR. The reported value will be transformed by $\log_{10}(X+1)$, where X is the reported number of RNA copies/ μ L. The transformed values will be summarized with descriptive statistics (number of observations, mean, standard deviation, minimum, maximum, median) by treatment group. A Satterthwaite T-test will be used to test the hypotheses

$$H_0: \mu_{NTZ} = \mu_{Ctl}$$
$$H_1: \mu_{NTZ} \neq \mu_{Ctl},$$

where μ_{NTZ} and μ_{Ctl} respectively represent the mean $\log_{10}(\text{RNA copies}/\mu\text{L})$ concentrations for the NTZ and placebo groups. A 95% confidence interval for the difference in means will be provided.

4.2.2.4 Exploratory Analysis: Proportion of Subjects Hospitalized Due to COVID-19 or Complications Thereof

The cross-tabulation of Hospitalization due to COVID-19 illness or complications thereof versus treatment group will be provided, with conditional rates for each treatment group.

Hospitalization due to COVID-19 or complications thereof will be analyzed using a CMH test stratified by the randomization stratum with the appropriate continuity correction at an unadjusted α of 0.05. The hypotheses tested are

$$\begin{aligned} H_0: p_{NTZ} &= p_{Ctl} \\ H_1: p_{NTZ} &\neq p_{Ctl} \end{aligned}$$

where p_{NTZ} and p_{Ctl} respectively represent the rate at which NTZ subjects and placebo subjects are hospitalized due to COVID-19 illness or its consequences. The overall odds ratio and a 95% confidence interval for the odds ratio will be provided.

4.2.2.5 Exploratory Analysis: Proportion of Subjects with Mortality Due to COVID-19 or Complications Thereof

The cross-tabulation of Mortality due to COVID-19 illness or complications thereof versus treatment group will be provided, with conditional rates for each treatment group.

Mortality due to COVID-19 or complications thereof will be analyzed using a CMH test stratified by the randomization stratum with the appropriate continuity correction at an unadjusted α of 0.05. The hypotheses tested are

$$\begin{aligned} H_0: p_{NTZ} &= p_{Ctl} \\ H_1: p_{NTZ} &\neq p_{Ctl} \end{aligned}$$

where p_{NTZ} and p_{Ctl} respectively represent the rate at which NTZ subjects and placebo subjects die due to COVID-19 illness or its consequences. The overall odds ratio and a 95% confidence interval for the odds ratio will be provided.

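### Exploratory viral RNA endpoint: the documents disagree on which follow-up swabs are quantified, give no value for a negative or below-limit swab, and do not use baseline RNA as a covariate

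*Protocol*

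**What the plan says.** **Which swabs are quantified.** Protocol 8.2.2.3: "Nasopharyngeal swab samples testing positive for SARS-CoV-2 will be subjected to quantitative RT-PCR for analysis of quantitative changes in viral RNA". SAP 4.2.2.3: "Viral RNA levels will be determined for the Day 4 and Day 10 nasopharyngeal swabs by quantitative RT-PCR", with no restriction to positives. Under Protocol 8.2.2.2, a subject positive at Baseline has both later swabs tested by Aptima, so a negative follow-up result is possible.

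**Value for a negative swab.** SAP 4.2.2.3 analyses log10(X+1), where X is the reported copy number. The transform is defined at X = 0, but neither document says that a negative swab receives 0, and no quantification limit is stated. The imputation rules in SAP 2.3 concern dates only.

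**The test.** Protocol 9.4.1: "Mean changes from baseline in quantitative SARS-CoV-2 RNA measured by RT-PCR at Day 4 and Day 10 will be compared using a t-test". SAP 4.2.2.3: "A Satterthwaite T-test will be used to test the hypotheses". Neither names a covariate or strata.

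**Change or level.** The objective in Protocol 3 is "The change from baseline in quantitative SARS-CoV-2 RNA measured by RT-PCR at each of Days 4 and 10", and SAP 4.1.2 defines the variable as "Change from baseline of quantitative SARS-CoV-2 RNA measured by RT-PCR at Days 4 and 10". The heading of SAP 4.2.2.3 and the title of Table 14.2.5.2 also say change. The hypotheses in SAP 4.2.2.3, however, define the two means as log10 "concentrations for the NTZ and placebo groups. A 95% confidence interval for the difference in means will be provided", which is a level.

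**Population.** Protocol 9.4.1 bases efficacy on randomised subjects "who receive at least one dose of study medication and are positive for SARS-CoV-2 by Aptima® SARS-CoV-2 Assay at Baseline", and SAP 2.2.1 makes the matching ITI population primary for efficacy. SAP 4.2.2 opens by assigning all key secondary and exploratory analyses to ITT, and Tables 14.2.5.1 and 14.2.5.2 carry the ITT label.

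**The concern.** A programmer could exclude negative swabs for want of a measured value, set them to zero, or set them to an assay limit. Each choice gives a different estimate when the drug works. Exclusion is the least defensible: clearing virus is an outcome the drug is meant to affect, so comparing only subjects still positive conditions on a post-randomisation result.

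Baseline-positive swabs are quantified anyway under Protocol 8.2.2.3. Using that value as a covariate would sharpen the estimate at almost no cost, and the plan does not do so.

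Timing adds some weight. SAP 2.4.1 allows unblinded tables to reach the sponsor before the RT-PCR results exist. A rule for negative swabs settled after that point would be settled by people who could know the trial's outcome.

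**Working it through.** **Plan's own figure.** There is none to reproduce. No SD, effect, correlation, positivity rate or detection limit is given for this endpoint. The only input from the documents is 175 per arm (SAP 1.3), a size chosen for the primary endpoint. Everything else below is assumed.

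**Step 1: cost of not using baseline as a covariate.** With equal SDs and correlation rho, in units of the SD squared, the change score has variance 2(1 - rho) and ANCOVA has 1 - rho². The ratio is 2(1 - rho)/(1 - rho²) = 2/(1 + rho): 2/1.2 = 1.67, 2/1.5 = 1.33 and 2/1.7 = 1.18 at rho 0.2, 0.5 and 0.7.

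**Step 2: effect of the swab rule on the estimate.** Assume normal log10 RNA with SD s = 1.5, baseline mean 3, detection at 0, and a true follow-up difference (placebo minus NTZ) of 0.50. For follow-up mean m, let P = Phi(m/s) be the share still positive and L = phi(m/s)/P.

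- Positives-only change: 0.50 + s(1 - rho)(L placebo - L NTZ).
- Negatives set to X = 0: the difference between arms in mP + s·phi(m/s).

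For means 1.0 and 0.5, P is 0.75 and 0.63, and L is 0.427 and 0.599. At rho 0.2 the positives-only estimate is 0.50 + 1.5 × 0.8 × (0.4274 - 0.5985) = 0.29. With X = 0 it is 1.227 - 0.881 = 0.345 (0.346 from these rounded terms), at every rho. Subjects dropped per arm are 175(1 - P) = 44 on placebo and 65 on NTZ.

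| Follow-up means (placebo/NTZ) | Positive (placebo/NTZ) | Dropped (placebo/NTZ) | Positives-only change, rho 0.2/0.5/0.7 | X = 0 |
|---|---|---|---|---|
| 1.0/0.5 | 75/63% | 44/65 | 0.29/0.37/0.42 | 0.345 |
| 1.5/1.0 | 84/75% | 28/44 | 0.33/0.40/0.44 | 0.40 |
| 3.0/2.5 | 98/95% | 4/8 | 0.44/0.46/0.48 | 0.48 |

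Both rules pull the estimate below 0.50. In the first two cases at rho 0.5 to 0.7, X = 0 attenuates as much as positives-only change, or more. A large-sample simulation gave the same figures. Repeating it with the exact log10(X+1) transform and positive baselines only moved no estimate by more than about 0.02.

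**Step 3: power.** Simulated at 175 per arm, 2,000 runs per cell, two-sided 0.05, Monte Carlo error about 1 point. Entries are for rho 0.2/0.5/0.7.

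| Analysis | 75/63% positive | 84/75% positive | 98/95% positive |
|---|---|---|---|
| Change t-test, positives only | 28/54/82% | 36/63/89% | 57/82/97% |
| Change t-test, X = 0 | 48/64/80% | 56/74/90% | 67/87/97% |
| ANCOVA, positives only | 46/61/82% | 57/74/91% | 81/91/99% |
| ANCOVA, X = 0 | 83/90/96% | 86/92/98% | 87/95/99% |

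Much of the gain comes from the covariate, but in the first two cases ANCOVA on positives alone gives up a good part of it. A left-censored model with baseline as covariate estimated 0.49 to 0.50 throughout. The randomisation factors were not simulated.

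**Step 4: no drug effect.** In 4,000 runs at rho 0.5 with equal arms, the positives-only t-test rejected 5.1% of the time.

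**Step 5: a different set of assumptions.** With SD 2, limit 1 log10, rho 0.3, a true difference of 1.0, and 30% (placebo) and 49% (NTZ) negative, the change t-test gives:

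- negatives dropped: 0.59, power 52%;
- set to 0: 0.79, power 92%;
- set to the limit: 0.60, power 77%.

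The assigned value matters as well as the decision to keep the swabs.

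**The case against.** **The positives-only rule is a laboratory instruction.** Protocol 8.2.2.3 says what is assayed; no passage removes unquantified subjects from the analysis. The +1 in the SAP transform suggests that zeros were expected. This stands in part: a reader might infer that the plan excludes subjects who cleared virus, and the documents do not say so. They do not assign a value either, so exclusion remains one possible outcome.

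**Baseline RNA is used.** A reader might infer from the hypothesis wording that baseline is ignored. The objective, Protocol 9.4.1, SAP 4.1.2, the section heading and the table title all say change, so baseline enters by subtraction. This stands; the shortfall is only that it is not a covariate.

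**ANCOVA is a preference.** A Welch t-test on change is valid here, and the precision advantage shrinks as rho rises. It stands that this corrects no error, but the gain is nearly free.

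**The swab rule may not matter, and X = 0 is no cure.** Under the t-test at rho 0.7, power is almost the same either way (82/80%, 89/90%, 97/97%), and X = 0 is not reliably closer to 0.50. Both statements are correct. The left-censored model's accuracy is also partly circular, because the data were generated from that model.

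**Timing and population have limited effect.** The laboratory stays blind, and the re-run under SAP 2.4.1 only adds data. Baseline-negative subjects have no planned SARS-CoV-2 follow-up test, so the ITT label may change little in practice. With expected positivity of 50 to 75%, however, 25 to 50% of ITT would be baseline-negative, and giving all of them X = 0 would dilute the contrast.

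**Conclusion.** The point holds as a minor one. The protocol and SAP differ on which swabs are quantified, and neither gives a value for a negative or below-limit follow-up swab. Under the assumptions above, the choice moves the estimate by up to about 0.07 log10 on a true 0.50 in the first two cases (for example 0.33 against 0.40, or 0.42 against 0.345), in either direction depending on rho. It moves t-test power by up to 20 points (28% against 48%, or 36% against 56%). Leaving baseline out as a covariate inflates variance by a factor of 1.18 to 1.67 over rho 0.7 to 0.2. The hypothesis wording and the ITT assignment conflict with the rest of the plan.

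A reader might infer a biased or invalid test. The documents and the check do not support that: omitting the covariate costs precision only, and type I error is intact when there is no effect. The swab rule matters for the estimate when there is one. The endpoint is exploratory and outside the formal testing sequence, clearance has its own stratified CMH test, and the primary and key secondary conclusions do not depend on it. All magnitudes rest on an assumed SD, correlation, positivity and detection limit.

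**What to change.** In SAP 4.2.2.3:

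- Analyse log10(X+1) RNA at each day by ANCOVA on treatment, baseline log10(X+1) RNA and the randomisation factors. Report the adjusted difference with its 95% CI. Record this as a change from the t-test in Protocol 9.4.1; the unadjusted t-test can stay as supportive.
- State that all tested follow-up swabs of baseline-positive subjects stay in the analysis. Give Aptima-negative swabs, and Aptima-positive swabs below the RT-PCR quantification limit, one stated value (for example X = 0). Add a matching sentence to Protocol 8.2.2.3.
- Because any fixed value also attenuates the difference, add a left-censored model with the same covariates as a sensitivity analysis, censored at the stated limit.
- Reword the means in the hypotheses as change from baseline. With baseline as a covariate, the treatment coefficient is the same for level and change.

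Elsewhere, amend the ITT sentence that opens SAP 4.2.2 as it applies to this endpoint, and relabel Tables 14.2.5.1 and 14.2.5.2 as ITI. Fix all of this before any unblinded tables are released under SAP 2.4.1.

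The cost is SAP wording and programming, one protocol sentence and one documented change of method. No extra assays are needed: positive baseline swabs are already quantified, and follow-up swabs of baseline-positive subjects already have an Aptima result.
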